1. AMENDMENT HISTORY

Amendment No.	Protocol Version No.	Date issued	Author(s) of changes	Details of Changes made
1	3.0	25/5/2016	[name]	

2. SYNOPSIS

Study Title	Childhood Asthma Management in Primary Care: Implementation Of Exhaled Nitric Oxide and Spirometry Testing (CHAMPIONS study)
Trial Design	Implementation study
Trial Participants	Children aged 5-16 years
Planned Sample Size	1000
Follow-up duration	Postal questionnaire at 3-6 months
Planned Trial Period	2 years
Primary Objective	The main objective for this study will be to evaluate the training and capacity requirements of primary care sites in order for them to be able to deliver routine spirometry and FeNO testing for children aged 5-16 years as recommended by draft NICE guidelines.
Secondary Objectives	
The secondary outcomes measured relate to the impact of implementing the new NICE guidelines on the processes and outcomes of childhood asthma care and will include:
 
 1. The number of children in which a diagnosis of asthma can be confirmed using spirometry and FeNO testing 2. The number of misdiagnoses identified using lung function tests 3. The impact of implementation to health economics

3. ABBREVIATIONS

ACT	Asthma Control Test
AE	Adverse event
AR	Adverse reaction
CCG	Clinical Commissioning Group
CI	Chief Investigator
CRA	Clinical Research Associate (Monitor)
CRF	Case Report Form
CRN	Clinical Research Network
CRO	Contract Research Organisation
CT	Clinical Trials
EC	Ethics Committee (see REC)
FeNO	Fractional Exhaled Nitric Oxide
GCP	Good Clinical Practice
GLI	Global Lung Function Initiative
GP	General Practitioner
GTAC	Gene Therapy Advisory Committee
HCA	Health Care Assistant
ICF	Informed Consent Form
NHS	National Health Service
NICE	National Institute of Health and Care Excellence
NRES	National Research Ethics Service
PI	Principal Investigator
PIL/S	Participant/ Patient Information Leaflet/Sheet
PN	Practice Nurse
R&D	NHS Trust R&D Department
REC	Research Ethics Committee
SAE	Serious Adverse Event
SAR	Serious Adverse Reaction
SOP	Standard Operating Procedure
SUSAR	Suspected Unexpected Serious Adverse Reactions
TMF	Trial Master File

4. BACKGROUND AND RATIONALE

In the UK the latest figures indicate that a total of 4.1 million people receive treatment for asthma (1). Of these approximately 1.1 million are children over the age of 5 years, which is the equivalent of one in ten children in the UK (2).

Despite the common nature of asthma there is no gold standard test available to diagnose the condition. The diagnosis is generally based on a thorough clinical history taken by an experienced clinician. Studies in adult populations however suggest that many are misdiagnosed including over and under-diagnosis of asthma (3-6). Over-diagnosis may affect up to 30% of adults diagnosed with asthma (3) and can result in inappropriate and unnecessary use of asthma medications and increased healthcare costs. Under-diagnosis often results in poor control and reduced quality of life.

Under-diagnosis and under-treatment of childhood asthma in primary care have been reported from several European countries (7-8) including the UK (9). The International Study of Asthma and Allergies in Childhood (ISAAC) for example reported that one-third of children aged 12 to 14 years in Great Britain with frequent night time wheezing had no diagnosis of asthma (9). Getting the diagnosis right in children is important because children have the highest asthma hospital admission rates for any age-group with asthma and under-diagnosis is associated with poor asthma control. Moreover, inappropriate treatment of children who do not have asthma with asthma medications can lead to unnecessary side-effects including a decreased growth velocity resulting from long-term inhaled corticosteroid use.

A recent draft NICE guideline (10) for asthma diagnosis and monitoring, originally due for publication in July 2015, recommends the use of objective tests including spirometry and FeNO testing to diagnose asthma in all patients 5 years and older under investigation for asthma. Recent BTS/SIGN asthma guidelines published in October 2014 also state that spirometry is superior to peak flow measurements, currently the most widely used lung function test in primary care in the management of asthma (11).

Proposed NICE asthma diagnostic algorithm: For children aged 5 to 16 years and adults with symptoms of asthma the draft guideline recommends spirometry testing for diagnosis and where obstructive spirometry is present bronchodilator reversibility should be considered. FeNO, an inflammatory marker in exhaled breath linked with asthma, should be considered where spirometry is normal and where obstructive spirometry does not reverse with bronchodilators. The proposed NICE guidance for diagnosis of asthma is summarised below.

[figure not shown]
Diagnostic criteria for asthma in children aged 5-16 years:

- Clinical symptoms compatible with the diagnosis

- Objective tests including
 - Obstructive spirometry
 - Reversibility following short acting beta-2-agonists ($\geq 12\%$ increase in FEV₁)
 - Raised FeNO (≥ 35 ppb)
 - Peak flow variability ($>20\%$)

No single positive test is diagnostic for asthma

Draft NICE diagnostic algorithm for children aged 5-16 years with suspected asthma

Asthma monitoring: Spirometry should be done in adults with asthma and considered in children at every asthma review.

Spirometry: Spirometry is available in primary care and performed in adults with COPD where it is already part of the Quality Outcome Framework (QOF). NICE and BTS/SIGN state that spirometry is preferable to measurement of peak expiratory flow because it allows clearer identification of airflow obstruction, and the results are less dependent on effort.

Spirometry is however only rarely performed in children in primary care. Children benefit from visual incentive spirometry which requires a special spirometer usually not available in GP

practices. Interpretation of spirometry in children also requires a slightly different approach. Consequently, practice nurses/health care assistants (PN/HCA) usually have no experience in performing and interpreting spirometry in children, but could be trained to do so. The amount of training required and how best to deliver it are currently not known and addressing these knowledge gaps is one of the main implementation research questions.

FeNO testing: The draft NICE asthma guideline recommends that FeNO testing should be considered in children with symptoms and under investigation for asthma who have normal spirometry and those with obstructive spirometry but no bronchodilator reversibility. FeNO testing in the diagnosis of asthma has been the topic of a separate NICE review published in April 2014, recommending FeNO testing as an option to diagnose asthma in children and adults with an intermediate probability of asthma in combination with other diagnostic options (12) There will be limited training requirements to perform the test and NICE have provided clear-cut guidelines for interpretation of the results.

Preliminary data/focus group meeting results:

Primary care practice focus group meeting: In preliminary work leading up to this protocol we conducted a focus group meeting with GPs, PN/HCAs and managers to explore attitudes, feasibility and potential barriers to implementation which have informed our implementation study proposal. Generally practice health care workers attitude towards spirometry and FeNO testing was favourable but training and capacity issues were raised as a major barrier to implementation.

One major finding from the focus group meetings was that the number of children aged 5-16 years on the asthma register appeared to be much lower than what would be predicted from epidemiological data. This data was gathered to understand how many children would need spirometry as part of their asthma review. Further inquiry of the practice database revealed that the number of children prescribed regular inhaled corticosteroids was more than double the number on the practice asthma register and when children were added who had been prescribed at least two short acting beta-2 agonist inhalers in the previous 12 months the total number of children rose to approximately 4-times the number on the asthma register and very close to the 10% of children predicted by epidemiological data.

These findings resulted from a small sample of children and may not be generalizable. Nonetheless, practice GPs felt that the 'cleaning up' of the asthma register by establishing the diagnosis or misdiagnosis of asthma would be a positive effect resulting from the objective tests recommended by NICE.

CCGs and commissioning: In two meetings with [name], the principal commissioner of children's services and CCG GP leads there was clear support for the proposed study to inform implementation of the NICE guideline into Leicestershire GP practices. This was identified as a priority funding area for discussion in the next financial year.

Leicestershire Partnership Trust Respiratory Specialist Nurse Lead: The implementation study was discussed with [name], lead respiratory nurse in the Leicestershire Partnership Trust (LPT). The LPT respiratory nurse team helped implement and continues to support the implementation of spirometry testing for patients with COPD in Leicestershire primary care practices. [name] experience with implementation informed the study protocol and advised on how best to start addressing the training needs and barriers to implementation and joined the study team.

The current training package is usually delivered to individual PN/HCAs during a 2-hour training session preceding a joint COPD clinic and consists of a PowerPoint presentation on performance and interpretation of spirometry followed by hands on training. Depending on the level of experience of the PN/HCA the spirometry testing of patients in the clinic will be either supervised or supported where necessary or, where the PN/HCA is naïve to spirometry, she/he will observe at least 10 patients before performing supervised spirometry. Nurses are referred to 'A Guide to Performing Quality Assured Diagnostic Spirometry' (13) for further information on spirometry testing. The guide is supported by the NHS, Asthma UK, Primary Care Respiratory Society UK, BTS, the Association for Respiratory Technology & Physiology and others but its emphasis is on the testing in adults with COPD. Additionally, in order to obtain LPT accreditation the PN/HCA has to send in 10 spirometry tracings of which 8 have to comply with Association for Respiratory Technology & Physiology standards and be correctly interpreted. Group sessions for several practices located in close proximity are offered up to four times per year and one to one sessions are offered as appropriate with GPs who interpret the spirometry.

Rationale

The use of the lung function tests in children is already routinely done in hospitals, has been shown to be safe in children and is now being recommended (at least in draft guidance) by NICE. As such, our research question is not whether we should use spirometry and FeNO testing in primary care, indeed they are not viewed as research interventions in this study; the question is – how can this be achieved?

Therefore the primary rationale for this study is to identify the training needs and capacity requirements of primary care practices in order for objective lung function testing to be made available for all children with suspected or confirmed asthma cared for in the non-hospital setting.

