5.2 Secondary Objectives

The secondary objectives relate to investigating the impact of implementing the new NICE guidelines on the processes and outcomes of childhood asthma care and will include:

1. The number of children in which a diagnosis of asthma can be confirmed using spirometry and FeNO testing
2. The number of misdiagnoses identified using lung function tests
3. The impact of implementation to health economics

[figure not shown]

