Incentive spirometry: Forced expiratory manoeuvres will be performed according to American Thoracic Society/European Respiratory Society standards (15,16). Children will be invited to perform a forced expiratory manoeuvre at least three times with a maximum of eight attempts. Where readings are within 5% of each other the recorded value is the best of these three readings. Achieving such reproducibility can be difficult in younger children and we will then use the best effort as the recorded values. Incentive spirometry will be used in all children, whereby visual aids are provided on the spirometer screen like for example a series of candles have to be blown out encouraging the child to breathe out hard for longer. This technique is very successful, even in young children. The PN/HCA will assess the forced expiratory volume in 1 second (FEV1) and the FEV1/FVC ratio. Where the FEV1/FVC ratio is lower than the GLI threshold or where FEV1 is <80% predicted they will perform reversibility testing using Salbutamol 400 micrograms (4 puffs) given via spacer and repeat the forced expiratory manoeuvre after 15 minutes. Any change in FEV1 of $\geq 12\%$ will be taken as demonstrating reversible airway narrowing and this in conjunction with the clinical history will be taken as diagnostic for the presence of asthma. The data and the lung function trace will be recorded on the practice electronic patient records and the GP informed.

FeNO measurements: Will be taken in all children five years and older using a NIOX MINO (Aerocrine, Sweden), which is a hand-held device with a mouthpiece. The result of the FeNO concentration in exhaled breath is available immediately in parts per billion (ppb) and we will use the cut-off value of 35ppb and above as diagnostic for asthma as per NICE guideline.

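### Section 4 says one positive test is not diagnostic, Section 8.3 takes raised FeNO alone as diagnostic, and a child with normal spirometry can show only that one positive test, so the counts for objectives 1 and 2 depend on which section is applied

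*Combined protocol and SAP*

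**What the plan says.** Section 4 (Proposed NICE asthma diagnostic algorithm) gives the criteria for ages 5-16 as compatible symptoms plus objective tests. It lists four tests: obstructive spirometry, "Reversibility following short acting beta-2-agonists" (a rise in FEV1 of at least 12%), FeNO of at least 35 ppb, and "Peak flow variability" above 20%. It then states: "No single positive test is diagnostic for asthma". The FeNO paragraph of the same section describes FeNO as an option used together with other diagnostic options.

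Section 8.3 sets out what is done at the review. On reversibility: "Where the FEV1/FVC ratio is lower than the GLI threshold or where FEV1 is <80% predicted they will perform reversibility testing". FeNO measurements: "Will be taken in all children five years and older", although the same section elsewhere limits FeNO to children in whom it is indicated. Section 8.3 also gives its own reading of results. A FeNO at or above 35 ppb is taken as diagnostic, with NICE cited as the authority. An FEV1 change of at least 12% is diagnostic when combined with the clinical history.

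Peak flow appears only in Section 4. It is not among the assessments (8.2, 8.3), the follow-up data (8.5), or the training content and outcome data (9.1).

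Objective 1 in Section 5.2 is: "The number of children in which a diagnosis of asthma can be confirmed using spirometry and FeNO testing". Objective 2 is the number of misdiagnoses found with lung function tests. Section 11.1 plans tests on both counts. Neither section says how many positive tests make a confirmed case, what makes a misdiagnosis, or how a test not done by design is handled.

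**The concern.** The two sections give different answers for the same child. A child with normal spirometry and raised FeNO has asthma under Section 8.3. If Section 4 is read as needing more than one positive test, that child is unconfirmed, and no result at the review could have changed this, because no second test that could be positive was offered. The data would then record two different things alike: a child tested and found negative on a second test, and a child never given one.

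Both counts are exposed. Inclusion (Section 7.2) is by asthma register, inhaler prescription or documented exacerbation, so many participants already carry an asthma label or asthma treatment. For them an unconfirmed result could easily be reported as a misdiagnosis. Section 5.2 presents these counts as the impact of implementing the guideline, and Section 4 reports that practices hope to clean up their registers with such results. A single published number would rest on a rule that the protocol has not settled.

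**Working it through.** The plan states no figure for this point, so there is none to reproduce. The check enumerates possible results under the Section 8.3 testing rules, with FeNO done in all children.

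**Step 1. Most positive tests that can be observed, out of the four in Section 4**

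| Spirometry result | Tests that can be positive | Maximum |
|---|---|---|
| Ratio not low, FEV1 at least 80% | FeNO | 1 |
| Ratio not low, FEV1 below 80% | reversibility, FeNO | 2 |
| Ratio low | obstruction, reversibility, FeNO | 3 |

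**Step 2. Normal spirometry: the 8 possible true patterns (1 = would be positive if tested)**

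| Reversibility | FeNO | Peak flow variability | Positives observed | Positives if all four tests were done | Section 8.3 FeNO rule |
|---|---|---|---|---|---|
| 0 | 0 | 0 | 0 | 0 | not asthma |
| 0 | 0 | 1 | 0 | 1 | not asthma |
| 1 | 0 | 0 | 0 | 1 | not asthma |
| 1 | 0 | 1 | 0 | 2 | not asthma |
| 0 | 1 | 0 | 1 | 1 | asthma |
| 0 | 1 | 1 | 1 | 2 | asthma |
| 1 | 1 | 0 | 1 | 2 | asthma |
| 1 | 1 | 1 | 1 | 3 | asthma |

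In 4 of the 8 patterns at least two tests would be positive if all were done, but only 0 or 1 is observed. One of those four is FeNO-negative and so looks the same as a child with nothing positive. Under a more-than-one rule none of the 8 can be confirmed; under Section 8.3 four are. These are counts of logical patterns, not shares of children.

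**Step 3. How the rules bound objective 1**

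Let L be the number of children with at least two positive tests, U the number with at least one, and M the Section 8.3 count (reversibility or FeNO positive, assuming a compatible history).

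- Any two of obstruction, reversibility and FeNO include reversibility or FeNO, so L ≤ M.
- Every child in M has a positive test, so M ≤ U.
- U − L is the number with exactly one positive test.
- M − L is those positive on FeNO only or reversibility only. U − M is those positive on obstruction only.

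**Step 4. Size, under assumed rates**

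The documents give no test rates. Assume 60-90% of children have normal spirometry and 15-35% of those have raised FeNO. The contribution of normal-spirometry children to M − L is n × P(normal) × P(raised FeNO, given normal):

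- Low: 1000 × 0.60 × 0.15 = 90 (9.0%)
- High: 1000 × 0.90 × 0.35 = 315 (31.5%)

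Children with abnormal spirometry and exactly one positive test would add to this.

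For scale, the standard error of a proportion at n = 1000 and p = 0.5 is √(0.5 × 0.5 / 1000) = 0.0158, or 1.6 points. This treats children as independent. With only 3-6 practices (Section 6.1), clustering could make it larger, so it is not a ceiling.

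**The case against.** The strongest reply is that Section 4 only summarises draft guidance in the background, while Section 8.3 is the operative text. On that view a child with normal spirometry and raised FeNO is simply counted as asthma. This stands in part. A reader might infer that such children cannot be scored at all, or that the confirmed count is capped by design. Neither follows, because the child is unconfirmed under one section and a case under the other. But Section 8.3 cites the guideline as its authority, and the protocol's own account of that guideline says otherwise, so the conflict remains.

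A more-than-one rule is also an inference. Section 4 introduces its tests as a non-exhaustive list, puts symptoms first, gives no minimum count, and its algorithm figure is not available here. One positive test plus symptoms is a possible reading. That is a reason to state the definition.

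A reader might take conditional reversibility testing as a departure from the guidance. The documents do not support this: Section 4 itself ties reversibility to "obstructive spirometry", and Section 8.3 broadly follows it. Nor is leaving out peak flow clearly an oversight, since objective 1 and the capacity work are confined to spirometry and FeNO. Peak flow variability is, however, one of the four tests in the criteria that the study sets out to implement.

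Finally, nothing says that an unconfirmed child will be counted as a misdiagnosis, and Section 9.1 separately records whether diagnoses changed. That is correct. The risk comes from the missing definition, not from a stated rule.

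**Conclusion.** The point holds in this form: the counts for objectives 1 and 2 depend on an unreconciled difference between Sections 4 and 8.3. For children with normal spirometry, the testing scheme cannot separate an unconfirmed diagnosis from a second test not done. The limit of one positive test follows from the text. The statement that these children can never be confirmed also needs the more-than-one reading of Section 4.

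The documents do not give the size. The figure of 90 to 315 per 1000 holds only under the assumed rates. It measures the gap between the two rules among children with normal spirometry. A reader might take it as the effect of omitting peak flow or reversibility. It is not: that would need the positivity of those tests among children with raised FeNO, and no such rate is given. The shift comes from classification, so recruiting more children would not reduce it.

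**What to change.** Reconcile Sections 4 and 8.3, and write the case definitions for confirmed and misdiagnosed into 5.2 and 11.1 before analysis, including how tests not done are treated.

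- **Objective 1.** Report a range. The lower bound counts children with more than one positive test and the upper bound counts those with any positive test, with the Section 8.3 count shown between them. Report separately the number with exactly one positive test, split by which tests were not done.
- **Objective 2, in the sense of over-diagnosis.** Do not count a child with any positive test as a misdiagnosis. Present children negative on every test performed as having no objective evidence on those tests. This is an upper bound on misdiagnosis, because peak flow variability, and often reversibility, was not tested. Simply splitting off the one-positive group would still leave FeNO-negative children with untested items open to being called misdiagnosed. Show the diagnosis changes recorded under Section 9.1 alongside.
- **Capacity.** State that the estimate in Section 9.1 covers spirometry and FeNO only.

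The cost is analysis wording and a derived variable. No new test or change in care is needed. The drawback is that the headline count becomes a range.

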5. OBJECTIVES

5.1 Primary Objectives

The main objective for this study will be to evaluate the training and capacity requirements of primary care sites in order for them to be able to deliver routine spirometry and FeNO testing for children with suspected or presumed asthma.

5.2 Secondary Objectives

The secondary objectives relate to investigating the impact of implementing the new NICE guidelines on the processes and outcomes of childhood asthma care and will include:

1. The number of children in which a diagnosis of asthma can be confirmed using spirometry and FeNO testing
2. The number of misdiagnoses identified using lung function tests
3. The impact of implementation to health economics

[figure not shown]
